TABLES INCLUDED IN THE TEXT

	Page
Table 1: Schedule of Assessments	13
Table 2: Definition of Responder and Non-Responder for Primary Endpoint	24

LIST OF ABBREVIATIONS AND DEFINITION OF TERMS

Abbreviation	Definition
AE	Adverse event
ALT	Alanine aminotransferase
ANC	Absolute neutrophil count
AST	Aspartate aminotransferase
ATC	Anatomic therapeutic class
BUN	Blood urea nitrogen
CBC	Complete blood count
CI	Confidence interval
CL	Clearance
CRF	Case report form
CSR	Clinical study report
CTCAE	Common Terminology Criteria for Adverse Events
DNA	Deoxyribonucleic acid
ECG	Electrocardiogram
ICH	International Council for Harmonisation
IEC	Independent Ethics Committee
IRB	Institutional Review Board
ITT	Intent-to-treat
MedDRA	Medical Dictionary for Regulatory Activities
QTc interval	QT interval corrected for heart rate
Rel Day	Relative study day
SAP	Statistical analysis plan
SD	Standard deviation
SI	International System of Units
VC	Vital capacity
WHO	World Health Organization

1.1. Introduction and Objectives

1.1.1. Introduction

Infection with human papillomavirus (HPV) can lead to malignant neoplasia, localized primarily in the ano-genital area and aero-digestive tract, in both men and women. Human papillomavirus types tropic to mucosal tissues are classified into high-risk (HR), based on their potential to cause cancer, and low-risk (LR) (causing generally benign lesions). In the United States (US), approximately 14 million new genital HPV infections occur annually, and approximately half of these infections are with a high-risk HPV type (HR-HPV) and thus can cause cancer [1]. In U.S. adults through age 59 years, about 25% of men and 20% of women have genital HR-HPV infection [2]. Human papillomavirus causes more cancers than any other virus. In US archival tissues of cancers diagnosed from 1993 to 2005, HPV deoxyribonucleic acid (DNA) was detected in 68.8% of vulvar, 90.6% of cervical, 91.1% of anal, 75.0% of vaginal, 70.1% of oropharyngeal (OP), 63.3% of penile, 32.0% of oral cavity, and 20.9% of laryngeal cancers, as well as in 98.8% of cervical cancer in situ (CCIS) [3]. An average of over 30,000 cases per year of HPV-attributable cancer were diagnosed during the period from 2008 through 2012 in the US [4]. Human papillomavirus-16 and HPV-18 are the most significant among HR types since they are responsible for most HPV-caused cancers [3].

With regard to anal cancer, about 95% of cases are caused by HPV, and most of those cases are caused by HPV-16 [5,6]; with some caused by HPV-18 and perhaps other HPV genotypes [1]. An estimated 8,300 new cases of anal cancer in the US are diagnosed each year (for 2017), with an estimated 1,280 deaths annually due to this cancer [7]. In Canada, the latest available data is for 2013, during which 580 new cases of anal cancer were diagnosed and 144 persons died due to anal cancer [8].

VGX-3100 contains plasmids that target HPV-16 E6/E7 and HPV-18 E6/E7 antigens. The plasmids were designed and constructed using proprietary synthetic vaccine (SynConTM) technology. This process involves synthetically deriving consensus genes across multiple strains and optimizing DNA inserts at the genetic level to allow high expression in human cells. Together, VGX-3100 and the CELLECTRATM device represent an integrated Investigational Product (IP) designed as a non-surgical treatment of HPV-16/18-related anal or anal/peri-anal high grade squamous intraepithelial lesion (HSIL; AIN2, AIN3, PAIN2, and PAIN3) via an immune response directed against HPV-16/18.

A total dose of 6 mg VGX-3100 DNA has been selected for this study based on previous human experience with VGX-3100, preclinical data with VGX-3100 and other DNA vaccines, and the safety and immunogenicity data generated in the HPV-001, HPV-003, and HPV- 101 studies. In the HPV-001 trial, the 6 mg dose was delivered IM followed by EP, which showed trends toward higher response rates and magnitudes of interferon- γ (IFN- γ) enzyme-linked immunospot assay (ELISpot) responses compared with the low (0.6 mg) and mid-dose (2 mg) cohorts without significant safety issues.

1.1.2. Statistical Analysis Plan Objectives

This statistical analysis plan (SAP) is designed to outline the methods to be used in the analysis of study data to answer the study objectives. Populations for analysis, data handling rules, statistical methods, and formats for data presentation are provided. The statistical analyses and summary tabulations described in this SAP will provide the basis for the results sections of the clinical study report (CSR) for this trial.

This SAP will also outline any differences in the currently planned analytical objectives relative to those planned in the study protocol.

1.1.3. Study Objectives

1.1.5.1. Primary Objectives

The primary objective is to determine the efficacy of 3 doses of VGX-3100 with respect to combined histopathologic regression of anal or anal/peri-anal HSIL and virologic clearance of HPV-16 and/or HPV-18.

1.1.5.2. Secondary Objectives

The secondary objectives include the following:

- To evaluate the safety and tolerability of VGX-3100 delivered IM followed by EP
- To determine the efficacy of 3 doses of VGX-3100 as measured by histologic regression of anal or anal/peri-anal HSIL
- To determine the efficacy of 3 doses of VGX-3100 as measured by virologic clearance of HPV-16 and/or HPV-18 by testing from lesion tissue
- To determine the efficacy of 3 doses VGX-3100 as measured by virologic clearance of HPV-16 and/or HPV-18 by intra-anal swab testing
- To determine the efficacy of 3 doses of VGX-3100 as measured by complete histopathologic regression of anal or anal/peri-anal HSIL to normal tissue
- To determine the efficacy of 3 doses of VGX-3100 as measured by histopathologic non-progression of anal or anal/peri-anal HSIL
- To describe the efficacy of VGX-3100 for partial responders, as measured by reduction in the number of intra-anal and/or peri-anal lesion(s), as applicable and the reduction in the size of peri-anal qualifying lesion(s), if present, and for whom the disease has not progressed according to Investigator judgment in subjects who did not have anal or anal/peri-anal HSIL lesion resolution at Week 36
- To determine the cellular immune response following administration of VGX-3100 at post dose 3, and after additional dosing compared to baseline

- To determine the efficacy of 3 doses of VGX-3100 with respect to histopathologic regression of anal or anal/peri-anal HSIL or virologic clearance of HPV-16 and/or HPV-18

1.1.5.3. Exploratory Objectives

The exploratory objectives include the following:

- To describe the long-term efficacy of VGX-3100 with respect to combined histopathologic regression of anal or anal/peri-anal HSIL and virologic clearance of HPV-16 and/or HPV-18
- To describe the long-term efficacy of VGX-3100, as measured by histologic regression of anal or anal/peri-anal HSIL
- To describe the long-term efficacy of VGX-3100, as measured by virologic clearance of HPV-16 and/or HPV-18 by testing from lesion tissue
- To describe the long-term efficacy of VGX-3100, as measured by virologic clearance of HPV-16 and/or HPV-18 by intra-anal swab testing
- To evaluate tissue immune responses to VGX-3100 in intra-anal and/or peri-anal samples
- To describe the clearance of HPV-16 and/or HPV-18 infection from non-anal anatomic locations
- To describe the association of microRNA (miRNA) profile, previous anoscopy, cytology, and HPV testing results with Week 36 histologic regression
- To describe the patient reported outcomes (PRO) for subjects treated with VGX-3100
- To determine the humoral and cellular immune response following administration of VGX-3100 at post dose 3, and after additional dosing compared to baseline
- To determine the long-term efficacy of VGX-3100 with respect to histopathologic regression of anal or anal/peri-anal HSIL or virologic clearance of HPV-16 and/or HPV-18

1.2. Study Design

1.2.1. Synopsis of Study Design

HPV-203 is a Phase 2, open-label efficacy study of VGX-3100 (DNA plasmids encoding E6 and E7 proteins of HPV types 16 and 18) administered by IM injection followed by EP in adult men and women who are HIV negative with histologically confirmed anal or anal/peri-anal

HSIL associated with HPV-16 and/or HPV-18. Approximately 24 subjects will receive at least 3 doses of VGX-3100. Each dose of VGX-3100 will be administered IM in a 1-mL volume followed immediately by EP.

To be eligible for the study, subjects must consent to participate and agree to the collection of anal lesion tissue samples for anal cytology and genotyping, a Digital Anal Rectal Examination (DARE), blood samples for immunologic assessments, high-resolution anoscopy (HRA) and HRA-guided biopsies. All intra-anal and/or peri-anal lesion(s) of adequate size ($\geq 4\text{mm}$) will be biopsied at Screening. Biopsy slides will be sent to a Pathology Adjudication Committee (PAC) for evaluation before enrollment. To be eligible for enrollment, the PAC must assign the diagnosis of anal or anal/peri-anal HSIL (AIN2, AIN3, PAIN2, PAIN3) based on the biopsy sample(s). Subjects must also have intra-anal and/or peri-anal lesion tissue test positive for HPV genotype 16 and/or 18 to be eligible for participation in the study.

Depending upon their disposition with regard to histologic and lesion area changes during the trial, all eligible subjects who consent to participate in the HPV-203 study will receive at least three doses of VGX-3100 (6 mg in 1 mL) administered IM (deltoid, preferred site, or anterolateral quadriceps, alternate site), each followed immediately by EP with the CELLECTRA™ 5PSP device. The first study treatment will be administered on Day 0, the second at Week 4, and the third at Week 12. Partial response to VGX-3100 may still be of medical importance by being able to limit the extent of surgery necessary. For partial responders at Week 36, a fourth dose may be administered at Week 40.

To assess quality of life and related impacts on subjects, PRO instruments will be provided and will include the Short Form Health Survey version 2 (SF-36v2™), the EQ-5D-5L, and 2 additional PRO questions assessing quality of life after surgery or biopsy.

The total duration of the study is up to 10 weeks for the screening period and up to 88 weeks for the treatment and follow-up periods.

1.2.2. Randomization Methodology

This is an open-label trial, and therefore, site personnel, individual subjects, and INOVIO or its representative trial personnel will be aware of the treatment allocations for this trial. Randomization does not apply.

1.2.3. Stopping Rules and Unblinding

No blinding will be done for this study as the study is open-label.

If any of the following situations occur, further enrollment and study treatments will be halted until a thorough review has been conducted by the Medical Monitor and Principal Investigator for the trial, the Data Safety Monitoring Board (DSMB), and the Institutional Review Board (IRB) / Ethics Committee (EC) (if applicable):

- If at any time during a study one-third (1/3) or more of the subjects experience an adverse event of special interest (AESI), verified per protocol definition

- If any serious adverse event (SAE; or potentially life-threatening adverse event [AE]) or death verified as related to study treatment occurs
- If 3 or more subjects in this study experience the same Grade 3 or 4 unexpected AE, verified per protocol definition and assessed as related to study treatment
- In the event of 2 identical, unexpected, Grade 4 toxicities, verified per protocol definition and assessed as related to study treatment

The sponsor or designee will notify all investigators and IRBs/EC (if required) regarding the outcome of any investigation stemming from a Study Pause.

1.2.4. Study Procedures

The schedule of assessments, as outlined in the study protocol, is provided in [Table 1](#)

Table 1: Schedule of Assessments

Study Action				Screening (-10 wk. to -1d)	Day 0								
Informed consent	X												
Medical History/Demographics	X												
Medications (prior/concomitant)	X	X		X		X	X	X	X	X	X	X	
Socio-behavioral assessment	X									X		X ¹⁵	X
Inclusion/Exclusion criteria ¹	X	X											
Physical exam (PE)/assessment ²	X	X		X		X	X	X	X	X	X	X	X
Vital signs	X ³	X		X		X	X	X	X	X	X	X	X
Screening safety (12 lead ECG, laboratories) ⁴	X												
Pregnancy Testing ⁵	X	X		X		X	X	X	X	X	X	X	X
HIV Ab by ELISA	X									X			
Blood immunologic samples	X ⁶	X ⁶					X ⁷		X ⁶				X ⁶
Oropharyngeal (OP) rinse		X		X			X	X	X			X	X
Vaginal, cervical, and penile swab		X		X			X	X	X			X	X
Intra-anal and/or peri-anal swab	X	X		X			X	X	X			X	X
Digital Anal Rectal Examination DARE ⁸	X	X		X			X	X	X			X	X
High Resolution Anoscopy (HRA) ⁹	X	X		X			X	X	X			X	X
Lesion photography ¹⁰	X	X		X			X	X	X			X	X
Biopsy ¹¹	X								X			X ¹⁸	

Study Action	Timeline											
	Screening (-10 wk. to -1d)	Day 0	8-14 days post dose 1 Phone Call	Week 4 (\pm 4 days)	8-14 days post dose 2 Phone Call	Week 12 (\pm 4 days)	Week 15 (\pm 1 Week)	Week 28 (\pm 1 Week)	Week 36 (\pm 1 Week)	Week 40 (\pm 1 Week)	8-14 days post dose 4 Phone Call	Week 64 (\pm 2 Weeks)
Inject VGX-3100 +EP ¹²	X		X	X		X				X ¹²		
Post treatment reaction assessment	X		X	X		X				X		
Distribute Participant Diary Card (PDC)	X		X	X		X				X		
Review PDC ¹³			X	X	X	X	X			X	X	
Patient Reported Outcomes (PROs) (SF-36v2 TM) (EQ-5D-5L) ¹⁴		X ¹⁶	X	X	X	X	X	X	X	X ¹⁷	X	X

1. Subject eligibility will be reconfirmed at every visit.
2. Full physical exam (PE) mandatory at Screening and study discharge (Week 88), otherwise targeted PE as determined by the Investigator or per subject complaints unless signs or symptoms dictate the need for a full PE.
3. Screening vital signs must include a measured height and weight and calculated body mass index (BMI) (Bodyweight in kilograms divided by height in meters squared). Weight will be collected at all dosing visits.
4. Screening 12-lead electrocardiogram (ECG), complete blood count (CBC), serum electrolytes, blood urea nitrogen (BUN), creatinine (Cr), glucose, alanine aminotransferase (ALT), and creatine phosphokinase (CPK) performed within 45 days before first dose administration.
5. Negative spot urine pregnancy test is required for female subjects at Screening, before each study treatment, high-resolution anoscopy (HRA), and biopsy/surgical excision; the pregnancy test at Week 40 would only be needed for subjects who receive an additional dose.
6. At least 34 mL (4 x 8.5-mL yellow [ACD] tubes) whole blood and 4 mL serum per time point. At least 68 mL whole blood and 8 mL serum should be collected before first dose.
7. At least 51 mL (6 x 8.5-mL yellow [ACD] tubes) whole blood and 4 mL serum should be collected at Week 15.
8. Digital Anal Rectal Examinations (DARE) are to be performed once cytology has been collected and before HRA.
9. An additional visit may be scheduled to perform HRA if worsening of disease is suspected. Biopsies should not be performed at any visit other than at entry (Screening) and Weeks 36 and 64 for Subgroup C unless the Investigator suspects invasive cancer. All biopsy samples and/or excision samples must be sent to the Pathology Adjudication Committee (PAC) for review.
10. Photography of qualifying lesion(s) must be performed before and after biopsy, and at all HRA examinations. If a pre-biopsy digital photograph is not available for a historical biopsy sample at Screening, a post-biopsy photo will be sufficient. Photographs of intra-anal lesion(s) will be for documentation purposes only. All qualifying peri-anal lesion(s) will be assessed using the ruler provided. The ruler should be placed in the field of vision and should be documented with photography at Screening, Day 0, and Weeks 4, 15, 28, 36, 64, and 88.
11. Tissue specimens (paraffin blocks) from all excised tissue lesion(s) that led to eligibility at study entry must be reviewed by the PAC, and residual tissue from entry and Weeks 36 and 64 specimen(s) (paraffin blocks) must be sent to the central laboratory for immune analysis and Human Papillomavirus (HPV) testing.
12. Potential dosing at Week 40 is applicable for partial responders only.
13. A phone call will be used to review the Participant Diary Card (PDC) with subjects within 8-14 days after doses 1 and 2. The subject will be expected to bring the PDC to the next visits for review. Subjects who receive an additional fourth dose will also have a phone call 8-14 days post dose 4 where the PDC will be reviewed. The subject should bring the PDC to the next visit.
14. Patient-reported outcome (PRO) measures (SF-36v2™ and EQ-5D-5L), plus 2 additional “global” questions will be assessed as described in Section 6.13 of the protocol.
15. This socio-behavioral assessment will only apply to those subjects in Subgroup C who receive a fourth dose of investigational product.
16. PROs at this time point must be administered before first dose of study drug.
17. PROs at this time point will only be for subjects who received a fourth dose of study drug.
18. Under Protocol Amendment 3.0, in addition to HSIL lesion(s) found at Screening, all visible lesions should have biopsy obtained at Week 64 and sent to the central pathology lab for review by PAC.

1.2.5. Efficacy, Pharmacokinetic, and Safety Parameters

1.2.5.1. Efficacy Parameters

The primary efficacy endpoint is the proportion of subjects with combined response outcome of histologic regression of anal or anal/peri-anal HSIL and virologic clearance of HPV-16/18 in intra-anal and/or peri-anal lesion tissue at Week 36. Histologic regression is defined as no evidence of anal or anal/peri-anal HSIL on histology. Virologic clearance is defined as no evidence of HPV-16 and/or HPV-18 by specific HPV testing.

Secondary efficacy endpoints are:

- Proportion of subjects with histologic regression at Week 36.
- Proportion of subjects with virologic clearance from intra-anal and/or peri-anal lesion tissue by type-specific HPV testing at Week 36.
- Proportion of subjects with virologic clearance from intra-anal swab by specific HPV testing at Week 36.
- Proportion of subjects with no evidence of anal or anal/peri-anal low-grade squamous intraepithelial lesion (LSIL) or HSIL (i.e. no evidence of AIN2, AIN3, PAIN2, PAIN3) on histology (i.e., biopsies or excisional treatment) at Week 36.
- Proportion of subjects with no progression of anal or anal/peri-anal HSIL to carcinoma from baseline on histology (i.e., biopsies or excisional treatment) at Week 36.
- Proportion of subjects with histologic regression or virologic clearance at Week 36 from intra-anal and/or peri-anal lesion tissue.
- Percent reduction in the number of qualifying intra-anal and/or perianal lesion(s) and the size of peri-anal lesion(s) as determined by the Investigator at Weeks 36, 64, and 88 compared with baseline. Results will also be classified as follows: no clinically significant lesion resolution (reduction in lesion area of 0%-25%), partial lesion area resolution (>25% and <100% reduction) and complete lesion resolution (no visible lesion).

Exploratory efficacy endpoints are:

- Proportion of subjects with histologic regression and virologic clearance at Week 64 by testing from intra-anal and/or peri-anal lesion tissue.
- Proportion of subjects with histologic regression at Week 64.
- Proportion of subjects with virologic clearance by testing from intra-anal and/or peri-anal lesion tissue at Week 64.
- Proportion of subjects with virologic clearance from intra-anal swab by specific HPV testing at Week 64 and Week 88.

- Proportion of subjects with virologic clearance from non-anal anatomic locations at Week 36.
- The relationship of miRNA profile (baseline and at Weeks 15 and 36), previous anoscopy, cytology and HPV testing results with histologic regression of anal or anal/peri-anal HSIL at Week 36.
- Proportion of subjects with histologic regression or virologic clearance from intra-anal and/or peri-anal tissue at Week 64.

To assess quality of life and related impacts on subjects, PRO instruments will be administered and will include the SF-36v2TM, the EQ-5D-5L, and additional PRO questions assessing quality of life after surgery or biopsy.

- SF-36v2TM - generically measures functional health and well-being, for physical and mental health; consists of 36 items covering 8 domains (Physical functioning, Role limitations due to physical problems, Bodily pain, General health, Vitality, Social functioning, Role limitations due to emotional problems, and Mental health).
- EQ-5D-5L - generically measures activities & general health status; consists of 6 items covering 6 domains (Mobility, Selfcare, Usual activity, Pain/discomfort, Anxiety/depression, and Global health status)

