- Non-progression of anal or anal/peri-anal HSIL will be investigated at Week 36 for all subjects and separately at Week 64 for all subjects and also stratified by subjects who receive 3 or 4 doses. Progression is defined as advancement to carcinoma by histology according to the PAC.

Reduction in surface area of qualifying intra-anal and/or peri-anal lesion(s) at Weeks 36, 64, and 88 will be assessed and determined by quantitative analysis of standardized pre-biopsy digital photographic imaging. The mean percent change and associated 95% t-distribution based CI will be presented. A lesion will be considered qualifying if it is confirmed to be HPV-16 and/or HPV-18 positive and is histologically confirmed as intra-anal and/or peri-anal HSIL by the PAC at Screening.

The relationship between regression/clearance endpoints at Week 36 will be summarized with the number and percentage of subjects meeting the endpoint separately by previous HRA results, previous cytology results, and previous HPV test results. The relationship between the

regression/clearance endpoints at Week 36 with miRNA profiles will be summarized with the median change from baseline in miRNA profiles by those who achieved versus those who did not achieve the endpoint. A subject's miRNA profile is based on change from baseline normalized result to the latest normalized result obtained before the time of the Week 36 endpoint.

By-subject listings will be provided for all efficacy-related parameters and results.

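### The lesion-resolution classes mix lesion area with lesion visibility, leaving a persisting intra-anal-only lesion without a class if area is peri-anal only, and SAP 4.3.2 contradicts that limit

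*SAP*

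**What the plan says.** For Weeks 36, 64 and 88, the secondary endpoint in SAP 1.2.5.1 is "Percent reduction in the number of qualifying intra-anal and/or perianal lesion(s) and the size of peri-anal lesion(s) as determined by the Investigator". Number therefore covers both sites, and size covers peri-anal lesions only. The results are then to be put into three classes. The lowest is "no clinically significant lesion resolution (reduction in lesion area of 0%-25" percent; the other two are "partial lesion area resolution (>25% and <100% reduction) and complete lesion resolution (no visible lesion".

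Two other places limit size in the same way. The secondary objectives (1.1.5.2) refer to "the reduction in the size of peri-anal qualifying lesion(s), if present". Table 1 footnote 10 (section 1.2.4) says "All qualifying peri-anal lesion(s) will be assessed using the ruler provided" and, for the other site, "Photographs of intra-anal lesion(s) will be for documentation purposes only".

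The analysis section, 4.3.2, differs: "Reduction in surface area of qualifying intra-anal and/or peri-anal lesion(s) at Weeks 36, 64, and 88 will be assessed", and this is to be "determined by quantitative analysis of standardized pre-biopsy digital photographic imaging". It plans a mean percent change with a confidence interval. It does not mention the three classes, their denominator, or any rule for classifying by lesion number.

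**The concern.** A set of response classes should use one measure on one set of lesions, so that every subject falls in exactly one class. Here the lower two classes need an area and the top class needs only that nothing is seen. If intra-anal lesions have no area, whether a subject with intra-anal disease only can be classed depends on the outcome: resolution has a class and persistence has none. That is more than a missing detail, because the rule as written sorts subjects by result.

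The table describing lesion response is at stake. Depending on how unclassed subjects are handled, it either overstates complete resolution or understates the other two rows. The SAP does not settle which, so two programmers could produce different tables from the same data.

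**Working it through.** The SAP states no figure for this classification, so there is nothing to reproduce. The check applies the three classes to each possible lesion state under the two readings that the SAP supports, and then illustrates the size.

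**Reading A: area exists for peri-anal lesions only (1.1.5.2, 1.2.5.1, footnote 10).**

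- Intra-anal disease only, lesion persists: there is no area, so no class applies, whether the lesion grew or shrank.
- Intra-anal disease only, lesion gone: *complete* can be assigned.
- Both sites, residual peri-anal lesion reduced by 0–25% or by more than 25% but less than 100%: classed normally.
- Both sites, peri-anal lesion gone, intra-anal lesion still visible: the area reduction is 100%, so not *partial*. It is not *complete* either if visibility covers both sites. No class.
- Peri-anal area increased: no class.

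**Reading B: area exists for both sites (4.3.2).**

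- Residual lesions at either site have an area, so persisting lesions are classed unless total area increased.
- If all qualifying lesions clear but a new lesion appears, the area reduction is 100% with a lesion in view. No class applies if visibility means any lesion.

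**How many failures have no class under Reading A.** Let *s* be the share of failures with intra-anal disease only and *q* the share of mixed-site failures that fit no class. The SAP gives neither. The unclassed share of failures is *s* + (1 − *s*) × *q*. With *q* assumed between 0 and 0.5:

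- *s* = 0: 0 to 0.50
- *s* = 0.25: 0.25 to 0.625
- *s* = 0.50: 0.50 to 0.75
- *s* = 0.75: 0.75 to 0.875
- *s* = 1: 1.00

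**Effect on the table under Reading A.** Inputs: 24 subjects (SAP 3.1). Assumed: 8 complete resolvers (one third), so 16 failures; resolution independent of site; a share *f* with intra-anal disease only; every other failure classed. Unclassed = *f* × 16; classed = 24 − *f* × 16.

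| *f* | Unclassed | Classed | Complete among classed | Complete among all 24 | *None* plus *partial* shown (true: 16) |
|---|---|---|---|---|---|
| 0.25 | 4 | 20 | 8/20 = 40% | 8/24 = 33% | 12 |
| 0.50 | 8 | 16 | 8/16 = 50% | 8/24 = 33% | 8 |
| 0.75 | 12 | 12 | 8/12 = 67% | 8/24 = 33% | 4 |

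Holding *f* at 0.50 and varying true resolution: at 20%, 4.8 / (24 − 0.5 × 19.2) = 4.8/14.4 = 33%; at 40%, 9.6 / (24 − 0.5 × 14.4) = 9.6/16.8 = 57%. Mixed-site subjects who fit no class would add to the unclassed count.

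**The case against.** The strongest reply is section 4.3.2. If area is measured at both sites, a persisting intra-anal lesion has an area, and a cleared peri-anal lesion beside a residual intra-anal one is a partial reduction in total area. Most of the gap then closes. This stands as far as it goes, but that section relies on photographs that footnote 10 reserves for documentation, and it conflicts with the size limit in 1.1.5.2 and 1.2.5.1. The contradiction is therefore part of the defect and does not resolve it.

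Second, the top class can be read as the 100% end of the same peri-anal area scale. A mixed-site subject whose peri-anal lesion clears is then *complete*, and subjects with intra-anal disease only fall outside the table whatever their outcome, so nothing is sorted by result. The wording allows this reading but does not state it.

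Third, 3.2 provides a category for missing data, and 2.1 and 4.3 make mITT the efficacy population. If unclassed subjects are shown as missing, the complete share stays at 8/24. That is correct, though the other two rows are then too small, and the SAP does not say that such subjects count as missing.

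Fourth, the loss is limited. Percent reduction in lesion number covers intra-anal lesions, and the partial-response objective in 1.1.5.2 rests on number, peri-anal size and investigator judgment, not on these classes. This stands too.

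**Conclusion.** The defect is real and of moderate weight. The classes use two measures without naming the lesions that count. On the sections that limit size to peri-anal lesions, every intra-anal-only failure lacks a class, while an intra-anal-only resolver can be *complete*. Some mixed-site failures also lack a class if visibility covers both sites. Section 4.3.2 contradicts those sections on whether intra-anal area exists at all.

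A reader might go further in three ways that the SAP does not support:

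- That most intra-anal or mixed-site failures go unclassed. Mixed-site subjects with a shrinking residual peri-anal lesion are classed, and no site mix is given. Entry by anal or anal/peri-anal HSIL does not show how many subjects have intra-anal disease only.
- That reported resolution will be inflated to 40–67%. Those figures need Reading A, the assumed 8 of 24, *f* between 0.25 and 0.75, and removal of unclassed subjects from the denominator. With a missing category the figure is 33%, and only the *none* and *partial* rows are understated.
- That the top class certainly covers all lesions at any site. This is an inference; 1.2.5.1 does not say.

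The endpoint is secondary and descriptive. No hypothesis test depends on it, and the primary analysis and sample size are unaffected.

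**What to change.** 1. Reconcile 4.3.2 with 1.1.5.2, 1.2.5.1 and footnote 10: either limit the area analysis to measured peri-anal lesions, or state that intra-anal area is measured and amend the other places to match.
2. If area is peri-anal only, apply the area classes only to subjects with a measured peri-anal lesion at baseline. Make 100% reduction the top class and add a class for increase.
3. Report intra-anal outcome by percent reduction in lesion number, which is already an endpoint in 1.2.5.1. Do not carry the area cut points over to counts: a subject with one lesion can only have a 0% or 100% reduction and could never be *partial*.
4. Report absence of visible lesions as a separate yes/no row over all mITT subjects, stating whether it covers qualifying lesions only or all lesions.
5. If intra-anal area is measured, still add the class for increase and state which lesions the top class covers.

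The cost is SAP wording and one extra small table, using lesion counts and peri-anal sizes that the endpoint already requires. The downside is possibly a less favourable resolution figure.
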